### 4.10.3 Vital Signs

Vital signs data (SBP, DBP, Pulse rate, respiratory rate and tympanic temperature) will be listed for individual subjects. Summary statistics of absolute (observed) values and changes from baseline will be calculated for each parameter and scheduled timepoint by treatment group. Clinically significant values for vital signs will be presented again in a separate listing.

Out-of-reference-range values will be flagged as high (H) or low (L) and as being clinically relevant or not: the number of subjects presenting out-of-range and clinically relevant values will be summarised.

The normal range for vital signs is displayed below:

Parameter	Normal Range
Temperature (tympanic)	35-38°C
Systolic Blood Pressure (Supine)	90-130 mmHg
Diastolic Blood Pressure (Supine)	40-90 mmHg
Pulse Rate (supine)	40-90 bpm
Respiratory Rate	8-20 breaths per min

### 4.10.4 Telemetry and Holter

Cardiac telemetry and Holter data (Start / End Date time and evaluation) will be listed by subject.

## Statistical Analysis Plan

### 4.10.5 Physical Examination

The physical examination performed at screening and at the Final Visit (Day 85) will be listed only and include an assessment of the following: general appearance, skin, eyes/ears/nose, neck, lymph nodes, throat, heart, lungs, abdomen, musculoskeletal system, and extremities. Symptom-directed physical examinations will be performed at all other time-points as needed, these will be included in the listings where available.

### 4.10.6 Electrocardiograms

TriPLICATE ECGs are performed at each timepoint ensuring the following criteria:

- Three consecutive evaluable ECGs;
- With maximum HR of 2 bpm difference;
- TriPLICATE is obtained between 1.5 to 4.5 minutes.

Due to above criteria, up to 10 ECGs can be acquired for a given timepoint. Typically, in most cases, the last 3 ECGs represent the triPLICATE which will be transferred to Clario for adjudication. If a triPLICATE could not be obtained (e.g. due to variable heart rate) then the last 3 ECGs are transferred for adjudication.

Adjudicated ECGs (Clario) will be used for analyses in the TFLs. Un-adjudicated ECGs (internal RPL) will be listed only. Details are as below.

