- p) Pre-dose, 4-hour post-dose and 8-hour post-dose on Day 1; time matched to dosing at all other time points. All PK sampling beyond Day 1 will be collected alongside a valid triplicate ECG
- q) Pre-dose on Day 1; time matched to dosing at all other time points.
- r) Pre-dose.

Table 5 Schedule of Assessments with detailed timepoints for 12-lead ECGs, vital signs, PK and PD samples

Study Day	Time (hours)	PK sampling (serum)	PD sampling (plasma)	Vital signs ^a	12-lead ECG ^b
	-2				X
	-1			X	X
	-0.5	X	X		X
	0.5			X	X
D1	1			X	X
	4	X		X	X
	5			X	X
	6			X	X
	7			X	X
	8	X		X	X
D2	24	X		X	X
D3	48	X		X	X
D4	72	X		X	X
D5	96	X		X	X
D6	120	X		X	X
D7	144	X		X	X
D8	168	X		X	X
D9	192	X			X
D10	216	X			X
D11	240	X			X
D12	264	X			X
D13	288	X		X	X
D14	312	X			X
D15	336	X		X	X
D22	504	X		X	X
D29	672	X		X	X

Study Day	Time (hours)	PK sampling (serum)	PD sampling (plasma)	Vital signs ^a	12-lead ECG ^b
D43	1008	X	X	X	X
D57	1344	X	X	X	X
D71	1680	X	X	X	X
D85	2016	X	X	X	X

a) Vital signs (respiratory rate, tympanic temperature, blood pressure and heart rate) will be measured after at least 5 minutes rest in supine position.
b) 12-lead ECGs (triplicate) will be measured after at least 10 minutes rest in supine position. ECGs will be time matched to occur before PK/PD blood sampling. ECGs collected on Day 22, Day 43, Day 57 and Day 71 will be collected for safety purposes only and will be reviewed by the Investigator. ECG data from these timepoints will be transferred and stored at the central ECG laboratory but will not be adjudicated unless requested by the Sponsor. ECGs collected on all other timepoints will be reviewed by the Investigator but will also be transferred and adjudicated by the central ECG laboratory. The outcome of the adjudication will be reported in the Clinical Study Report (CSR).

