7.8.3 Adjudication of 12-lead ECGs

ECG data will be transferred to a central ECG laboratory. ECGs from Day 22, Day 43, Day 57 and Day 71 will not be adjudicated initially, although adjudication of these ECGs may be performed later at the request of the Sponsor. ECGs from all

other timepoints will be adjudicated. Results from ECG adjudication will be transferred to RPL and be included in the study database.

7.8.4 24-hour Holter ECG

Holter recording will be performed during Screening Period days -21 to -2 as described in Table 4. Each electronic Holter ECG file will be downloaded onto the GE Gated Holter Analysis system. Holter data will be reported by a cardiac physiologist and reviewed by a Consultant Cardiologist. Ultimate decision for inclusion is at the discretion of the PI, in accordance with the study eligibility criteria.

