All unadjudicated ECG data (PR, QRS, QT, QTcB, QTcF and HR) and overall ECG evaluation will be listed. ECG data, along with changes from baseline, will be summarized using descriptive statistics (mean, median, standard deviation, minimum, maximum).

Furthermore, categorical analysis of QTcF data will be presented as follows:

- Absolute QTcF interval prolongation
 - QTcF interval > 450 ms
 - QTcF interval > 480 ms
 - QTcF interval > 500 ms
- Change from baseline in QTcF interval
 - QTcF interval increases from baseline > 30 ms
 - QTcF interval increases from baseline > 60 ms

Mean value of QTcF parameters will be plotted by dose group and time point. Out-of-reference-range values will be flagged as being clinically relevant or not. The

number of participants presenting out-of-range and clinically relevant values will be summarized.

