#### Secondary

- The safety endpoints will include adverse events (AEs), serious adverse events (SAEs), physical examinations, clinical laboratory assessments, vital signs, electrocardiograms (ECGs) including telemetry, withdrawal of participants, and early terminations. These endpoints will be assessed from baseline through Day 85 ± 5 days in the Safety Set.
- The immunogenicity endpoint includes UPB-101 anti-drug antibodies (ADAs) and presence of neutralizing antibodies (Nabs). These endpoints will

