## Adjudicated ECGs

All below analyses will be performed on adjudicated ECGs.

Adjudicated ECG parameters will be listed separately with above flags, with Clario evaluations where available.

For summary statistics an arithmetic mean value of the adjudicated triplicate ECG (where available) parameters will be used at each time-point. All below analyses will be performed using this set.

ECG data and changes from baseline will be summarised using descriptive statistics.

The change from baseline will be derived using the arithmetic mean value of each time-point triplicate minus baseline value, where baseline is the arithmetic mean of the pre-dose values of Day 1.

Furthermore, categorical analysis of QTcF data will be presented as follows:

- Absolute QTcF interval prolongation
  - QTcF interval > 450 ms to ≤ 480 ms
  - QTcF interval > 480 ms to ≤ 500 ms
  - QTcF interval > 500 ms
- Change from baseline in QTcF interval
  - QTcF interval increases from baseline > 30 msec to ≤ 60 msec
  - QTcF interval increases from baseline > 60 ms

The mean absolute value of QTcF will be plotted by treatment group and by time-point. The number of subjects presenting out-of-range and clinically relevant values will be summarised.

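### By default the SAP's ECG summaries and QTcF counts leave out Days 22, 43, 57 and 71 (4 of 6 follow-up visits), and neither the tables nor SAP 4.15 says so.

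*SAP*

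**What the plan says.** **Which readings the SAP analyses.** SAP 4.10.6 states "Adjudicated ECGs (Clario) will be used for analyses in the TFLs", and of the site's own readings "Un-adjudicated ECGs (internal RPL) will be listed only". Its subsection on adjudicated ECGs opens with "All below analyses will be performed on adjudicated ECGs". Under that sentence come the descriptive summaries, the changes from baseline, the QTcF bands (cut-points 450, 480 and 500 ms; rises above 30 and 60 ms), the mean QTcF plot and finally "The number of subjects presenting out-of-range and clinically relevant values will be summarised".

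**Which readings are adjudicated.** Protocol 7.8.3 says "ECGs from Day 22, Day 43, Day 57 and Day 71 will not be adjudicated initially". Table 5 footnote b in protocol 3.2 describes the same four visits as collected for safety and stored centrally; they "will not be adjudicated unless requested by the Sponsor". Table 6 in protocol 3.4 adds a second route, a safety issue that makes adjudication necessary. All other time points are adjudicated.

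**What the endpoint and the protocol's analysis section cover.** ECGs are among the secondary safety endpoints in SAP 2.2, of which it says "These endpoints will be assessed from baseline through Day 85". Protocol 10.5 first has the unadjudicated data listed, then says "ECG data, along with changes from baseline, will be summarized using descriptive statistics", followed by the QTcF categories. It neither limits these analyses to adjudicated readings nor excludes any visit.

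**What is recorded as changed.** SAP 4.15 lists two departures from the protocol, concerning PD and neutralizing antibodies. ECGs are not mentioned.

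**The concern.** Each rule is clear alone, but together they remove four visits from every ECG table without any sentence saying so. SAP 4.10.6 does not name the four visits. It describes triplicates at each time point being sent to the central laboratory for adjudication, so someone working from the SAP alone would expect the tables to cover every scheduled ECG.

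What is at stake is the reading of the QTcF outlier table. A participant whose only exceedance falls on Day 22, 43, 57 or 71 adds nothing to the counts unless those ECGs are adjudicated. A zero in that table would naturally be taken as a zero through Day 85, the stated end of the endpoint window. The triplicates needed to fill the gap are already in the schedule and read at the site.

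**Working it through.** The plan gives no figure to reproduce, and no power or sample-size formula applies. The check is a count from the schedule, plus a rough look at exposure.

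**Inputs.**
- Follow-up visits (protocol 3.1): Days 22, 29, 43, 57, 71 and 85, six in all.
- Not adjudicated by default (protocol 7.8.3, Table 5 footnote b, Table 6): Days 22, 43, 57 and 71.
- Post-dose ECG time points (Table 5): Day 1 at 0.5, 1, 4, 5, 6, 7 and 8 hours (7); Days 2 to 15 once daily (14); follow-up (6).
- Planned participants: 32.

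**Coverage.**
- Follow-up visits omitted: 4/6 = 66.7%. Days 29 and 85 remain.
- Post-dose time points: 7 + 14 + 6 = 27. Omitted: 4/27 = 14.8%. Remaining: 23/27 = 85.2%.
- Planned triplicates omitted: 4 × 32 = 128, out of 6 × 32 = 192 in follow-up and 27 × 32 = 864 post-dose.
- Intervals between scheduled ECGs after Day 15: 7, 7, 14, 14, 14 and 14 days. Between summarised ECGs: 29 − 15 = 14 and 85 − 29 = 56 days.

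**Exposure at omitted and retained visits (illustration only).** Half-life and tmax are redacted. The protocol calls follow-up to Day 85 about five half-lives, which suggests 84/5 = 16.8 days; a tmax of 5 to 10 days is an assumption. In a one-compartment model with first-order absorption, C(t) is proportional to exp(−ke·t) − exp(−ka·t). Here ke = ln 2/16.8 = 0.0413 per day, and ka is solved from tmax = ln(ka/ke)/(ka − ke), giving 0.565 per day (tmax 5) or 0.198 per day (tmax 10). Time t is study day minus 1.

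| Day | In adjudicated tables by default | % of Cmax, tmax 5 to 10 days |
|---|---|---|
| 15 | yes | 74–95 |
| 22 | no | 56–77 |
| 29 | yes | 42–59 |
| 43 | no | 23–34 |
| 57 | no | 13–19 |
| 71 | no | 7–11 |
| 85 | yes | 4–6 |

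Under these assumptions only Day 22 is a high-exposure omission, and it lies between two summarised visits. Days 43, 57 and 71 are all below the retained Day 29. The assumed peak falls within Days 1 to 15, which are fully summarised.

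**Are the two readings interchangeable?** SAP 4.10.6 gives separate reference ranges: QRS up to 120 ms at the site against 60–109 ms centrally. The QTcF upper limit is 450 ms in both. The SAP's ECG baseline, the mean of the Day 1 pre-dose values, is defined within the adjudicated set. A site-read change therefore needs a site-read baseline. Table 5 schedules three pre-dose ECGs on Day 1 (−2, −1 and −0.5 hours), so one can be formed.

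**The case against.** The strongest reply is that the split by visit is a deliberate protocol decision. The protocol labels these four visits as safety-only, links the CSR's adjudication output to the other time points, and repeats the split in three places. Using one central reader for the quantitative tables is a sound way to keep the readings consistent. This stands, and it is a good reason to keep the adjudicated tables as they are.

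A reader might go further and infer that a QTcF exceedance at these visits would be lost or go unnoticed. The documents do not support that. A research physician reviews every recorded ECG, and abnormal ones may be followed to resolution (protocol 7.8.2). Site values are listed with high/low flags and a clinical-relevance assessment (SAP 4.10.6). If a safety issue calls for adjudication, Table 6 commits to performing it and reporting it in the CSR, and the values would then qualify for the tables. A clinically important finding could also be reported as an adverse event.

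These safeguards leave part of the point standing. The documents set no QTcF threshold that automatically triggers adjudication, so entry to the tables depends on someone's decision. Results adjudicated at the Sponsor's request for another reason may go unreported in the CSR. A listing does not feed a categorical count. An isolated, asymptomatic rise above 30 ms is the most plausible case to be listed but not counted.

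It may also be said that protocol 10.5 already treats unadjudicated ECGs as listing material. It does require them to be listed, but it does not confine them to a listing, and its summary sentence carries no restriction.

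**Conclusion.** The point holds under the default plan. Unless the Sponsor requests adjudication or a safety issue requires it, the ECG summaries, QTcF categories, plot and out-of-range counts cover 2 of 6 follow-up visits and 23 of 27 post-dose time points, with a 56-day gap between Days 29 and 85. The endpoint is defined through Day 85, protocol 10.5 states no restriction, and SAP 4.15 records none.

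The consequence is modest. ECG is one component of a descriptive secondary safety endpoint with no formal test, protocol Table 2 reports no cardiovascular effects in human or nonclinical studies, and the primary PK comparison is unaffected. The exposure table might tempt a reader to conclude that the plan drops the visits that matter most for QT. It does not show that: it rests on an assumed half-life and tmax, and three of the four omitted visits have lower modelled exposure than the retained Day 29. The coverage counts need no such assumption; they come directly from the schedule.

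**What to change.** 1. Keep the adjudicated tables and plot as planned, and state in their titles or footnotes which visits they cover.
2. Add one separate table of site (RPL) readings for Days 22, 43, 57 and 71: triplicate means, change from the site-read pre-dose Day 1 mean, and QTcF counts at the existing cut-points (above 450, 480 and 500 ms; rises above 30 and 60 ms).
3. Do not merge these rows or counts with the central readings, because the reference ranges differ and a combined per-participant count would mix readers.
4. Record in SAP 4.15 that the main ECG tables are restricted to adjudicated readings.

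The cost is SAP wording and one additional table. No further ECGs or central readings are needed. The downside is a second reading source in the report, which must be clearly labelled.

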#### Un-adjudicated ECGs

All un-adjudicated ECG data (PR, QRS, QT, QTcB, QTcF and HR) including H/L flags and overall ECG evaluation will be listed only. Out-of-reference-range values will be flagged as clinically relevant or not. Reference ranges for RPL ECGs are as follows:

Parameter	Normal Range
Heart Rate (Supine)	40-90 bpm
PR Interval	120-200 ms
QRS duration	≤120 ms
QTcF	≤450 ms (Males & Females)

Clario's Reference Ranges are as follows:

Parameter	Normal Range
RR	600-1200
PR Interval	120-200 ms
QRS	60-109 ms

# Statistical Analysis Plan

QT	320 – 450 ms
QTcF or QTcB	320–450 ms (Males & Females)

## Adjudicated ECGs

All below analyses will be performed on adjudicated ECGs.

Adjudicated ECG parameters will be listed separately with above flags, with Clario evaluations where available.

For summary statistics an arithmetic mean value of the adjudicated triplicate ECG (where available) parameters will be used at each time-point. All below analyses will be performed using this set.

ECG data and changes from baseline will be summarised using descriptive statistics.

The change from baseline will be derived using the arithmetic mean value of each time-point triplicate minus baseline value, where baseline is the arithmetic mean of the pre-dose values of Day 1.

Furthermore, categorical analysis of QTcF data will be presented as follows:

- Absolute QTcF interval prolongation
  - QTcF interval > 450 ms to ≤ 480 ms
  - QTcF interval > 480 ms to ≤ 500 ms
  - QTcF interval > 500 ms
- Change from baseline in QTcF interval
  - QTcF interval increases from baseline > 30 msec to ≤ 60 msec
  - QTcF interval increases from baseline > 60 ms

The mean absolute value of QTcF will be plotted by treatment group and by time-point. The number of subjects presenting out-of-range and clinically relevant values will be summarised.

## 4.11 Pharmacokinetic Data Reporting

PK analyses from blood samples will be performed on the PK set and will be reported at each time point by treatment group (dose level). PK parameters will be presented as follows in the listing:  $C_{max}$  and  $t_{max}$  will be presented as given in the raw data; other PK parameters will be presented with 3 significant figures. Descriptive statistics for PK parameters will be presented with decimal places as appropriate for the particular parameter and treatment group. PK parameters with the exception of

$T_{max}$  and  $t_{1/2}$  will be reported to 3 significant figures.  $T_{max}$  and  $t_{1/2}$  will be reported to 2 decimal places.

Standard non-compartmental PK parameters for serum samples of UBP-101 will be estimated, and study drug exposure to UBP-101 will be summarised using continuous summary statistics. Concentrations will be listed and summarised by dose level and time point. Values excluded from table summaries will be flagged and included in the listing. Figures will present the individual and mean  $\pm$  SD concentration curves on both a linear and log scale. Figures will be presented by treatment group (dose level). The PK parameters will be listed for each subject and summarised for each dose level using descriptive statistics.

### *4.11.1 Values Below the Limit of Quantification and Missing Values*

If a BLQ value occurs in a profile before the first measurable concentration, it will be assigned a value of zero concentration. If a BLQ value (or consecutive BLQ values) occurs after a measurable concentration in a profile and is followed by a value above the lower level of quantification, then the appropriateness for omission of the BLQ value will be assessed following visual inspection of the plasma concentration versus time profile and set to missing. If a BLQ value (or consecutive BLQ values) occurs at the end of a collection profile (after the last quantifiable

# Statistical Analysis Plan

concentration), it will be assigned a value of "missing". If consecutive BLQ values occur at the start of a collection profile, the first will be assigned a value of zero and all subsequent BLQ values will be omitted.

## 4.11.2 Pharmacokinetic Parameters

The following PK parameters for UBP-101 will be calculated.

Parameter	Description
$C_{max}$	Maximum observed serum concentration
$T_{max}$	Time at which the maximum serum concentration occurs
$t_{1/2}$	Terminal half-life
$\lambda_z$	Terminal elimination rate constant obtained from linear regression of time vs log-concentration during the terminal elimination phase; using at least three time-points during the terminal elimination phase.
$AUC_{0-inf}$	Area under the serum concentration-time curve from time 0 extrapolated to infinite time
$AUC_{0-t}$	Area under the serum concentration curve from time zero up to the last quantifiable concentration
$AUC_{%extrap}$	Percentage of AUC that is due to extrapolation from $t$ last to infinity $((AUC_{0-inf} - AUC_{0-tlast})/AUC_{0-inf}) \times 100$
$CL/F$	Serum clearance after extravascular administration calculated as Dose/ $AUC_{0-inf}$
$V_z/F$	Apparent Volume of distribution after extravascular administration; calculated as...Dose/( $\lambda_z * AUC_{0-inf}$ )

The individual serum concentration data, and the actual time for UBP-101 administration and blood sampling will be used in the derivation of the PK parameters. If there is any doubt in the actual time a sample was taken, or if the actual sampling or dosing times are missing, then the scheduled time will be used.

$AUC_{0-t}$  and  $AUC_{0-inf}$  will be calculated using the linear/log trapezoidal method, applying the linear trapezoidal rule up to  $C_{max}$  and the log trapezoidal rule for the remainder of the curve. Samples below lower limit of quantification (LLOQ) prior to the first quantifiable concentration will be set to zero. Samples with concentrations

LLOQ after the first quantifiable concentration will be set to 'missing' and omitted from the analysis.

In the determination of  $\lambda_z$  (and  $AUC_{0-\infty}$ ), the following conditions should be met:

- A minimum of at least 3 data points in the terminal elimination phase, in which  $C_{max}$  is not included;
- The Adj-Rsq should be  $\geq 0.8$ , and
- $\%AUC_{extrap} < 20\%$ .

If these conditions are not met, the PK parameter will be flagged in the listings (together with those dependent on  $\lambda_z$ , such as  $t_{1/2}$ ,  $CL/F$  and  $V_z/F$ ) and they may be excluded from the summary statistics. The decision to include these parameters will be based on the decision of the Sponsor with input from the pharmacokineticist.

The following flags/footnotes may be applied to the PK parameters:

Flag	Footnote
a	Adj-Rsq of regression was $<0.8$
b	Extrapolated portion of $AUC_{0-\infty}$ $>20\%$
c	Insufficient post- $C_{max}$ data points for estimation of lambda-z
d	Entire profile BLQ, no pharmacokinetic parameters could be calculated
e	Regression line could not be fitted

Descriptive statistics for PK parameters will include number of observations, arithmetic mean, SD, CV, geometric mean, geometric CV, median, minimum, and maximum. Median and range will only be presented for  $T_{max}$ .

If serum concentrations are all BLQ, then PK parameter estimation and all subsequent statistical summaries will not be possible.

## 4.12 Pharmacodynamic Analyses

The analysis of pharmacodynamic (PD) data falls outside the scope of this SAP.

## 4.13 Immunogenicity Analyses

Immunogenicity (ADA) to UPB-101 will be explored (incidence and duration) for each treatment group using a three-tiered approach of screening, confirmatory, and titer.

ADA data will be listed for each participant. Samples which screen ADA-positive in the screening assay, will undergo a confirmatory assay to confirm the presence of ADA. Once confirmed as ADA-positive, the samples will be run in a titration assay to determine the level of ADA response. Summaries of positive ADA test results over time may be provided.

